12.0 Descriptive Factors

- 12.1 CD38⁺ expression: Positive ($\geq 30\%$) vs. negative ($< 30\%$).
- 12.2 Chromosomal anomalies as detected by FISH: 13q- vs. 12+ vs. 11q- vs. 17p- vs. other abnormality vs. normal karyotype.
- 12.3 *IGHV* mutation status: Mutated ($\geq 2\%$) vs. unmutated ($< 2\%$) vs. indeterminate.
- 12.4 ZAP-70 expression: Positive ($\geq 20\%$) vs. negative ($< 20\%$).
- 12.5 CD49d expression: Positive ($\geq 45\%$) vs. negative ($< 45\%$).

13.0 Treatment/Follow-up Decision at Evaluation of Patient

NOTE: As of Addendum 4, Event monitoring will no longer be required

- 13.1 After completion of the Day 43 response to vaccine evaluation, patients will discontinue treatment and enter one cycle of OBSERVATION (28 days after end of first cycle +/- 10 days) and then enter EVENT MONITORING.
- 13.2 If Lenalidomide is discontinued due to patient refusal or noncompliance, unacceptable toxicity, or intercurrent illness that makes treatment assessment difficult and the patient received the Prevnar 13 vaccine, they will receive their Day 43 response to vaccine evaluation at which point they will then enter one cycle of OBSERVATION (28 days after end of first cycle +/- 10 days) and then enter EVENT MONITORING.
- 13.3 If a patient on Arm A does not receive the Prevnar 13 vaccine, they will discontinue treatment and go directly to event monitoring per Section 18.0 of the protocol. If a patient on Arm B does not receive the Prevnar 13 vaccine, they will be deemed a cancel and will be removed from the study per Section 13.6 of the protocol.
- 13.4 A patient is deemed *ineligible* if after registration, it is determined that at the time of registration, the patient did not satisfy each and every eligibility criteria for study entry.
 - If the patient received treatment, the patient will go directly to event monitoring. All data up until the point of confirmation of ineligibility must be submitted. Event monitoring will be required per Section 18.0 of the protocol.
 - If the patient never received treatment, on-study material and the End of Active Treatment/Cancel Notification Form must be submitted. No further data submission is necessary.

Note: Due to the nature of the disease, if the patient is diagnosed with DLBCL within the first cycle of treatment, it will be assumed that the DLBCL was present at registration. The patient will be deemed ineligible per Sec 3.29c.
- 13.5 A patient is deemed a *major violation*, if protocol requirements regarding Lenalidomide treatment during Days 1-42 are severely violated such that evaluability for primary end point is questionable. All data up until the point of confirmation of a major violation

must be submitted. The patient will go directly to the event-monitoring phase of the study. Event monitoring will be required per Section 18.0 of the protocol.

- 13.6 A patient is deemed a *cancel* if he/she is removed from the study for any reason before any Lenalidomide (Arm A) or Plevnar (Arm B) is given . On-study material and the End of Active Treatment/Cancel Notification Form must be submitted. No further data submission is necessary.
- 13.7 A patient will be deemed a *flagr* if they received Lenalidomide and then failed to receive the Plevnar 13 vaccine (Arm A). Patients classified as a flagr will not be evaluable for response and will be replaced.

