9.0 Ancillary Treatment/Supportive Care

- 9.1 Antiemetics may be used at the discretion of the attending physician.
- 9.2 Blood products and growth factors should be utilized as clinically warranted and following institutional policies and recommendations. The use of growth factors should follow published guidelines of the : ASCO 2006 Update of Recommendations for the Use of White Blood Cell Growth Factors: An Evidence-Based Clinical Practice Guideline Journal of Clinical Oncology 2006;24:3187-3205.
- 9.3 Patients should receive full supportive care, including transfusions of blood and blood products, antibiotics, and antiemetics when appropriate. **Any blood transfusions administered must be irradiated blood products to reduce risk of transfusion mediated graft versus host disease in CLL patients receiving T-cell suppressive therapy. Leukocyte reduction of all blood products for patients on protocol is also required.** All blood products and concomitant medications such as antidiarrheals, analgesics, and/or antiemetics received from the first day of study treatment administration until 30 days after the final dose will be recorded in the medical records.
- 9.4 Diarrhea: This could be managed conservatively with loperamide. The recommended dose of loperamide is 4 mg at first onset, followed by 2 mg every 2-4 hours until diarrhea free (maximum 16 mg/day).
- In the event of grade 3 or 4 diarrhea, the following supportive measures are allowed: hydration, octreotide, and antidiarrheals.
- If diarrhea is severe (requiring intravenous rehydration) and/or associated with fever or severe neutropenia (grade 3 or 4), broad-spectrum antibiotics must be prescribed. Patients with severe diarrhea or any diarrhea associated with severe nausea or vomiting **should be hospitalized** for intravenous hydration and correction of electrolyte imbalances.
- 9.5 DVT prophylaxis: As indicated in section 7.0, all patients receiving lenalidomide (Arm A) will be required to take aspirin 325 mg/day for DVT Prophylaxis during the study as long as they are on lenalidomide. Patients who are intolerant or allergic to aspirin may use low molecular weight heparin at prophylactic dose level.

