10.4 Expedited Reporting Requirements for IND/IDE Agents

Phase 1 and Early Phase 2 Studies: Expedited Reporting Requirements for Adverse Events that Occur on Studies under an IND/IDE within 30 Days of the Last Administration of the Investigational Agent/Intervention^{1,2}

FDA REPORTING REQUIREMENTS FOR SERIOUS ADVERSE EVENTS (21 CFR Part 312) NOTE: Investigators MUST immediately report to the sponsor ANY Serious Adverse Events, whether or not they are considered related to the investigational agent(s)/intervention (21 CFR 312.64) An adverse event is considered serious if it results in ANY of the following outcomes:
 
 1) Death 2) A life-threatening adverse event 3) An adverse event that results in inpatient hospitalization or prolongation of existing hospitalization for ≥ 24 hours 4) A persistent or significant incapacity or substantial disruption of the ability to conduct normal life functions 5) A congenital anomaly/birth defect. 6) Important Medical Events (IME) that may not result in death, be life threatening, or require hospitalization may be considered serious when, based upon medical judgment, they may jeopardize the patient or subject and may require medical or surgical intervention to prevent one of the outcomes listed in this definition. (FDA, 21 CFR 312.32; ICH E2A and ICH E6). 		

ALL SERIOUS adverse events that meet the above criteria MUST be immediately reported to the sponsor within the timeframes detailed in the table below.
		
Hospitalization	Grade 1 and Grade 2 Timeframes	Grade 3-5 Timeframes
Resulting in Hospitalization ≥ 24 hrs	7 Calendar Days	24-Hour 3 Calendar Days
Not resulting in Hospitalization ≥ 24 hrs	Not required	

NOTE: Protocol specific exceptions to expedited reporting of serious adverse events are found in Section 10.41 of the protocol. Expedited AE reporting timelines are defined as:
 
 ○ “24-Hour; 3 Calendar Days” - The AE must initially be reported within 24 hours of learning of the AE, followed by a complete expedited report within 3 calendar days of the initial 24-hour report. ○ “7 Calendar Days” - A complete expedited report on the AE must be submitted within 7 calendar days of learning of the AE. 		

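### Sections 13.3 to 13.5 route some treated patients past the remaining safety visits into a discontinued event-monitoring phase, ending scheduled capture of non-serious and laboratory toxicity

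*Combined protocol and SAP*

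**What the plan says.** Section 13.2 keeps a patient who stops lenalidomide early on the Day 43 evaluation and the Observation cycle, provided the vaccine was given. Three other groups are treated differently.

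- **Arm A, vaccine not received (13.3):** "If a patient on Arm A does not receive the Prevnar 13 vaccine, they will discontinue treatment and go directly to event monitoring". If such a patient has taken lenalidomide, 13.7 labels them a flagr.
- **Found ineligible after treatment (13.4):** "If the patient received treatment, the patient will go directly to event monitoring".
- **Major violation (13.5):** "The patient will go directly to the event-monitoring phase of the study".

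All three point to Section 18.0 for event monitoring, and 13.4 and 13.5 add that it is required. The note that opens Section 13.0 says otherwise: "As of Addendum 4, Event monitoring will no longer be required". The note under the follow-up table in 18.1 repeats it. Section 7.2 requires a return to the consenting institution at Day 15 and Day 43 and makes no exception for any of these groups.

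The Section 4.0 test schedule places an AE assessment, physical exam and CBC at both Day 43 and Observation, with chemistry also at Day 43. Section 10.6 ties routine AE grading to Day 15, Day 43 and Observation.

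**The concern.** Whether a patient keeps the later safety visits depends on having been vaccinated and on administrative status, not on having taken lenalidomide. A patient with drug exposure can therefore leave scheduled follow-up while the protocol's own post-dose windows are still open. Section 10.4 covers serious events "within 30 Days of the Last Administration of the Investigational Agent/Intervention", and 9.3 has blood products and concomitant medications followed "from the first day of study treatment administration until 30 days after the final dose will be recorded in the medical records".

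The instructions also conflict. For a flagr or a major violation confirmed before Day 43, a site can read 7.2 as requiring the visit, 13.3 or 13.5 as bypassing it, and the 13.0 note as removing the place the patient is sent to.

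The arms are not affected equally. An unvaccinated Arm B patient is a cancel (13.3). Flagr applies only to Arm A (13.7), and major violation is defined by lenalidomide treatment (13.5). Only the ineligible route (13.4) can also take in treated Arm B patients. Shortened follow-up therefore falls mostly on Arm A and pulls its recorded AE rate downward.

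**Working it through.** **1. The routes side by side**

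| Group | Day 43 and Observation | In the 16.323 AE set? |
|---|---|---|
| Vaccinated, lenalidomide stopped early (13.2) | Both kept | Yes, if eligible |
| Arm A, took lenalidomide, no vaccine (13.3, 13.7) | Neither stated | Yes, if eligible |
| Treated, found ineligible (13.4) | None stated after confirmation | No |
| Major violation (13.5) | None stated after confirmation | Yes, if eligible |

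Section 16.323 counts eligible patients who started treatment. It takes each patient's highest recorded grade and gives no rule for shortened follow-up. I read that as leaving an unrecorded later event out of the numerator while the patient stays in the denominator.

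**2. What stays reportable and what lapses**

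- *Stays:* all serious events within 30 days of last administration, and related ones afterwards (10.4); deaths (10.52); secondary malignancies (10.53); pregnancies (10.55).
- *Lapses as scheduled capture:* related grade 2 events (10.611) and non-serious grade 3-4 events (10.612).
- *Laboratory toxicity lapses too.* Section 10.41 leaves grade 3-4 anemia and low platelet, neutrophil, lymphocyte and white-cell counts to routine reporting when there is no hospitalization. Platelet and hemoglobin grades are derived from blood counts (10.6, Appendix IV), so without a CBC there is no grade.

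**3. Timing for one patient**

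Take a flagr whose last dose is at about Day 15. The 30-day window runs to Day 15 + 30 = Day 45. A Day 43 visit would fall 28 days after that dose. Under 13.3 the last scheduled AE assessment is Day 15, so none falls later in the window.

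**4. Size**

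Inputs from 16.22: 26 evaluable patients plus an allowance of 3 per arm. This gives 26 + 3 = 29 per arm and 2 × 29 = 58, which reproduces the stated maximum accrual. The allowance covers ineligibility, cancellation, major violation and missed vaccine together, so 3 is the planned total for a wider class than the one at issue.

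Extreme case: all 3 Arm A patients are treated, stay in the AE set, are routed out, and each has an event that is never recorded. The understatement is k/29:

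- k = 1: 1/29 = 3.4 percentage points
- k = 2: 2/29 = 6.9 points
- k = 3: 3/29 = 10.3 points

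Milder illustration: the 3 patients share the arm's true rate r and none of their events is recorded. The apparent rate is r × 26/29:

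- 25% shows as 22.4%
- 30% shows as 26.9%
- 40% shows as 35.9%

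These rates are assumptions; the documents give no expected AE rate for Arm A.

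**5. The safety rules**

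Section 16.353 compares grade 3-4 non-hematologic rates between arms, so non-serious grade 3 events that go unrecorded can affect it. Lost CBCs cannot. Section 16.352 fires at 4 of the first 15 (4/15 = 26.7%) and not at 3 (3/15 = 20.0%), but it counts only non-hematologic events of grade 4 or higher that are at least possibly related.

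**The case against.** A reader might infer that later toxicity in these patients goes unseen. The documents do not support that. Serious-event, death, pregnancy and malignancy reporting does not depend on visits, and 10.612 asks for grade 3-4 events whatever the attribution. Section 10.62 refers late events to a Forms Packet that is not among the documents. The 18.1 table also appears to call for a Nadir/Adverse Event form at end of treatment. All of this stands. It leaves a duty to report what the site learns, but no scheduled contact through which to learn of non-serious events or to obtain a blood count.

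A reader might also infer that one missed event could keep the 16.352 pause rule from firing. Arithmetically 3 seen plus 1 unseen would do it. However, the unseen event would have to be a related, non-hematologic event of grade 4 or higher that was either not serious or not reported. Most such events would be serious and subject to 24-hour notice.

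A third inference is that patients too unwell for the vaccine are systematically dropped. The 7.1 footnote treats a hold as a delay, and 8.3 gives the vaccine whether or not lenalidomide is reduced or omitted. Once vaccinated, the patient is back under 13.2.

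Four further points stand:

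- Ineligible patients and violations lose visits only if their status is confirmed first, and data up to confirmation are still due.
- Treated ineligible patients are outside the 16.323 set in any case.
- Dropping event monitoring adds little loss, since its 18.1 schedule has no AE form. The cause is bypassing Day 43 and Observation.
- Observation at Day 72 ± 10 falls 20 to 40 days after a Day 42 last dose, so that visit does not guarantee a full 30 days even for completers.

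**Conclusion.** The point holds in a limited form. The current text contradicts itself about where these patients go. Read as written, 13.3 to 13.5 end scheduled capture of non-serious grade 3-4 events, related grade 2 events and laboratory toxicity for patients routed out before Day 43 or Observation.

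The likely number is 0 to 3 of 29 Arm A patients, assuming the 16.22 allowance is about right. The flagr and major-violation patients among them stay in the AE denominator with truncated follow-up. The Arm A rates in 16.323, and to a lesser extent the 16.353 comparison, can therefore be understated. The 10.3-point figure is a ceiling that requires every allowance patient to be treated, counted and have an unrecorded event; zero is within the realistic range.

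An effect on 16.352 is unlikely. The vaccine-response endpoint is not affected, because flagr and major-violation patients are already excluded from its evaluable set and ineligible patients do not qualify for it. This is a worthwhile, inexpensive clarification rather than a threat to the trial's conclusions.

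**What to change.** Reconcile 7.2, 13.0, 13.3 to 13.5 and 18.1, and remove event monitoring as a destination throughout Section 13.0.

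In 13.3, 13.4 and 13.5, state that any patient who has taken at least one dose of lenalidomide stays on whatever remains of the protocol's existing safety assessments (AE assessment, exam and CBC at Day 43 and Observation, as 13.2 already provides) and then goes off study. No newly timed visit is needed. Say explicitly in 13.4 what applies to treated Arm B patients found ineligible.

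The cost is protocol wording, plus asking a few patients who no longer contribute to the primary endpoint to attend visits already on the schedule. Sample size, power and treatment rules are unchanged.

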- 3.19d Able to take aspirin (81 or 325 mg) daily as prophylactic anticoagulation (patients intolerant to ASA may use warfarin or low molecular weight heparin).
- 3.19e Willing to provide blood samples for correlative research purposes (see Sections 6.12 and 14.0).
- 3.2 Exclusion Criteria
- 3.21 Palpable lymph nodes >3 cm in maximal dimension.
- 3.22 Any of the following because this study involves an investigational agent whose genotoxic, mutagenic and teratogenic effects on the developing fetus and newborn are unknown:
- Pregnant women
 - Nursing women

- Men or women of childbearing potential who are unwilling to employ adequate contraception
- 3.23 Any of the following comorbid conditions:
- New York Heart Association classification III or IV cardiovascular disease (Appendix I).
 - Recent myocardial infarction (≤ 30 days)
 - Uncontrolled infection
- 3.24 Immunocompromised patients and patients known to be HIV positive and currently receiving antiretroviral therapy. NOTE: Patients known to be HIV positive, but without clinical evidence of an immunocompromised state, are eligible for this trial.
- 3.25 Other active primary malignancy requiring treatment or limiting survival to ≤ 2 years prior to registration.
- 3.26 Any radiation therapy ≤ 28 days prior to registration.
- 3.27 Any major surgery ≤ 28 days prior to registration.
- 3.28 Current use of corticosteroids. EXCEPTION: Low doses of steroids (≤ 10 mg of prednisone or equivalent dose of other steroid) used for treatment of non-hematologic medical conditions. NOTE: Previous use of corticosteroids is allowed.
- 3.29a Active hemolytic anemia requiring immunosuppressive therapy or other pharmacologic treatment. NOTE: Patients who have a positive Coombs test but no evidence of hemolysis are NOT excluded from participation.
- 3.29b History of deep venous thromboses or pulmonary embolism ≤ 365 days prior to registration.
- 3.29c Co-existent diffuse large B-cell lymphoma (Richters Transformation)

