4.0 Test Schedule

Tests & Procedures	Active Monitoring Phase				
	Days Prior to Registration	Day 15 (+/- 3 days)	Day 28 (+/- 7 days)	Day 43 (+/- 4 days)	Observation: 28 days after end of first cycle (Day 72 +/- 10 days)
	≤14 days				
Medical history	X				
Adverse event assessment	X	X		X	X
Physical exam, including PS, weight and vital signs	X			X	X
Height	X				
Register in the REVLIMID REMS® program (Arm A only)	X ⁸				
Counseling for the REVLIMID REMS® program (Arm A only)			X		
Tumor measurement by physical exam	X ¹			X ¹	
Peripheral blood immunophenotyping by flow cytometry	X ²				
CBC with differential and reticulocytes	X	X		X	X
Serum pregnancy test	X ³	X ³	X ³	X ³	
Chemistry group (SGOT [AST], SGPT [ALT], total bilirubin, serum creatinine, calcium, alkaline phosphatase, uric acid, LDH, potassium)	X	X		X	
Glucose	X				
Direct bilirubin	X ⁷				
CD38	X ²				
ZAP-70	X ²				
IGHV	X ⁴				
CD49d	X ⁴				
Serum protein electrophoresis	X			X	
Beta-2-microglobulin	X				
Peripheral blood CLL FISH panel	X ⁶				
Serum quantitative immunoglobulins (IgG, IgA, IgM)	X			X	
Coombs test (monospecific direct coombs IgG and C3)	X				
EKG	X				
Quantitative T & B cells, peripheral blood	X			X	

Prevna 13 pneumococcal vaccination		X			
Research blood specimens (see Section 14.0)	X ^{5,R}	X ^{5,R}		X ^{5,R}	

1. Physical exam should measure the spleen and liver noting the maximal distance below the respective costal margins and should record the bidimensional diameter of the largest palpable node in each area of involvement including the following sites: left neck (sub-mandibular, cervical, supra-clavicular), right neck (sub-mandibular, cervical, supra-clavicular), left axillary, right axillary, left groin (inguinal, femoral) and right groin (inguinal, femoral).
 2. May be waived for patients who have previously had full flow immunophenotyping consistent with CLL performed at Mayo Clinic. Similarly, if the patient has previously had CD38 and/or ZAP-70 testing performed at Mayo Clinic, repeat assay is elective after discussing with the study chair.
 3. For women of childbearing potential only. Must follow pregnancy testing requirements as outlined in the Revlimid REMS® program material.
 4. If patient has previously had done clinically at Mayo Clinic, this does not need to be repeated.
 5. Blood specimens will be collected and submitted at baseline, Day 15 and Day 43. Kits are required.

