11.21 CLL/SLL: Disease status will be classified as one of the following using the criteria below which are based on the IWCLL criteria without the bone marrow biopsy results²⁴:

- progressive disease
- stable disease
- partial response
- clinical complete response (or clinical complete response with incomplete marrow recovery)

11.22 MBL: Disease status will be classified as one of the following criteria based on the IWCLL criteria for progressive disease:

- progressive disease
- not progressive disease

11.3 For the purposes of this study, patient's disease status will be evaluated at the time of the day 43 evaluation. Although the patient will be periodically seen Days 1 - 42, response evaluations will not occur on those dates.

NOTE: Information from CT scans is not considered in the standard classification of response.

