- 11.431 $\geq 50\%$ increase in the sum of the products of at least 2 lymph nodes (at least one node must be $\geq 2 \text{ cm}$) or the appearance of new palpable lymph nodes $>1.5 \text{ cm}$ **not due to a tumor flare**. Enlargements or the appearance of new nodes due to a tumor flare do NOT qualify as progression. If there is uncertainty as to whether lymph node enlargement at the Day 43 evaluation represents tumor flare, repeat examination 2-4 weeks after the protocol specified discontinuation of lenalidomide can be used to help make this determination.
- 11.432 $\geq 50\%$ increase in the size of the liver and/or spleen as determined by measurement below the respective costal margin on 2 consecutive determinations 2 weeks apart and with a minimum of a $\geq 2 \text{ cm}$ increase in size from baseline; or appearance of hepatomegaly or splenomegaly which was not previously present at baseline and **not due to a tumor**

flare. If there is uncertainty as to whether an increase in liver/spleen size at the Day 43 evaluation represents tumor flare, repeat examination 2-4 weeks after the protocol specified discontinuation of lenalidomide can be used to help make this determination.

- 11.433 Transformation to a more aggressive histology (e.g. Richter's transformation).

NOTE: If a patient develops DLBCL at any time, it will be considered progressive disease. If the patient develops any other hematological malignancy while on study, it will not be considered progressive disease.

- 11.434 $\geq 50\%$ increase in the absolute number of circulating lymphocytes NOT due to infection or tumor flare (taking as reference for progressive disease the smallest absolute lymphocyte count recorded since the treatment started).

- 11.435 Cytopenias due to lenalidomide toxicity will **not** be considered to represent disease progression. In the absence of progression as defined by 11.431, 11.432, 11.433, 11.434 above, the presence of a ≥ 2 g/dL decrease in HGB, or $\geq 50\%$ decrease in platelet count, or absolute neutrophil count will NOT be considered progression. Work-up of such decreases to exclude auto-immune hemolytic anemia, pure red cell aplasia, or idiopathic thrombocytopenic purpura (ITP) should be considered.

- 11.44 STABLE DISEASE (SD): Patients who do not meet criteria for CCR (or CCRi), PR, or PD will be classified as having "stable disease".

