16.321 Disease status by physical exam and complete blood counts will be evaluated in each patient. For CLL, each patient will be classified as CCR, CCRi, PR, SD, or PD per Section 11.2 at the time of the 6 week assessment of immune response. The distribution of disease status will be evaluated in each arm and will be summarized descriptively. Patients will be classified as responders (CCR, CCRi, PR) vs. non-responders (SD, PD). For MBL, patients will be classified as Not PD vs. PD. Differences in disease status response will be compared between the two arms using Fisher's exact test.

16.322 Time to treatment for progressive CLL will be defined as the time from the date of registration to the date of initiation of treatment for progressive CLL. The distribution of time to treatment will be estimated in each arm using the method of Kaplan-Meier. Time to treatment will be compared between the two arms using log-rank statistics.

16.323 Adverse Events: All eligible patients that have initiated treatment will be considered evaluable for assessing adverse event rate(s). Platelets and hemoglobin will be graded according to the Grading Scale for Hematologic Adverse Events in CLL Studies in Appendix IV. The maximum grade for each type of adverse event will be recorded for each patient, and frequency tables will be reviewed for each arm to determine

patterns. Additionally, the relationship of the adverse event(s) to the study treatment will be taken into consideration.

16.33 Correlative Analyses:

16.331 Pre-vaccination (day 15) and day 28 post-vaccination OPA GMTs for each serotype (4, 9V, 23F) will be reported in the vaccine and vaccine + lenalidomide groups. The fold-change in OPA GMT from baseline to 28 days post-vaccination will be evaluated for each serotype, where two-sample t-tests will be used to compare GMTs between the vaccine and vaccine + lenalidomide groups.

16.332 Pre-vaccination (day 15) and day 28 post-vaccination *Streptococcus pneumoniae* serotype specific IgG GMTs for each serotype (1, 3, 4, 5, 6B, 7F, 9V, 14, 18C, 19F, 19A, and 23) will be reported in the vaccine and vaccine + lenalidomide groups. The fold-change in quantitative IgG GMT from pre-vaccine (day 15) to 28 days post-vaccination will be evaluated for each serotype, where two-sample t-tests will be used to compare GMTs between the vaccine and vaccine + lenalidomide groups.

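### The 13.4 note turns first-cycle DLBCL into ineligibility, which conflicts with the 11.433 note and removes the patient from the primary response set and the adverse event tables

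*Combined protocol and SAP*

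**What the plan says.** Two notes in the protocol deal with DLBCL found after registration.

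- **Section 13.4, note:** when DLBCL is diagnosed during the first cycle, "it will be assumed that the DLBCL was present at registration". It continues: "The patient will be deemed ineligible per Sec 3.29c". The criterion invoked, 3.29c, excludes "Co-existent diffuse large B-cell lymphoma (Richters Transformation". The main text of 13.4 is stricter: it needs a determination, made after registration, that a criterion was not met at registration.
- **Section 11.433, note:** "If a patient develops DLBCL at any time, it will be considered progressive disease". There is no exception for the first cycle.

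Eligibility then decides who is analysed in two places. Sections 16.11 and 16.311 limit the primary response set to patients who meet the eligibility criteria, have consented and were vaccinated, less major treatment violations and those classed as flagr. For safety, 16.323 says: "All eligible patients that have initiated treatment will be considered evaluable for assessing adverse event rate(s".

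Under 13.4, a treated patient ruled ineligible goes straight to event monitoring, with data due only up to confirmation of ineligibility. Notes in 13.0 and 18.1 say that event monitoring has not been required since Addendum 4.

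**The concern.** The 13.4 note uses an outcome seen after randomisation to decide that a patient should never have been enrolled. It does so by assumption: no evidence that the lymphoma predates registration is asked for, and no rebuttal is allowed. The study requires no CT imaging or marrow biopsy (11.2), so its own data may be unable to test the assumption.

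Transformation while on lenalidomide is an event that readers of the safety results would expect to see. If the note is followed, that patient leaves the adverse event tables together with every other adverse event the patient had. The same case can also be read as progression under one section and as an enrolment error under another, with no text saying which governs.

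**Working it through.** **1. How far the two notes overlap.** The length of the first cycle is not defined in days. Section 7.1 gives treatment on Days 1-42, and the Section 4.0 test schedule places the next visit at "Observation: 28 days after end of first cycle (Day 72 +/- 10 days". If the cycle ends on Day 42, then 42 + 28 = 70, inside the printed window of 72 ± 10 (Days 62 to 82). So the first cycle appears to be the whole treatment period. Section 11.3 says that "patient's disease status will be evaluated at the time of the day 43 evaluation". The 13.4 presumption therefore covers essentially all the time in which a transformation could count as progression at Day 43.

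**2. Where a treated patient with first-cycle DLBCL ends up under the 13.4 note.**

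| Analysis or process | Stated population | Result |
|---|---|---|
| Primary response (16.11, 16.311) | Eligible and vaccinated | Out |
| Adverse event tables (16.323) | Eligible, treatment started | Out, with all other adverse events |
| Disease status (16.321) | Each patient | Not excluded by the text |
| Time to treatment (16.322) | None stated | Unspecified |
| Correlative analyses (16.33) | None stated | Unspecified |
| Stopping rule (16.352) | Treated patients | Counted if non-hematologic, grade 4 or higher and at least possibly related, or a related grade 5 |
| Expedited reporting (10.4) | Serious adverse events | Still applies |

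For the primary set, the note matters only after vaccination, because an unvaccinated patient is out of that set in any case.

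**3. Size for the primary test.** Start with the plan's own figure (16.21): 10% versus 30%, one-sided alpha 0.16, power 80%, pooled variance.

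- n per arm = [z(0.84) × √(2 × 0.2 × 0.8) + z(0.80) × √(0.1 × 0.9 + 0.3 × 0.7)]² / 0.2²
- = [0.9945 × 0.5657 + 0.8416 × 0.5477]² / 0.04 = 26.2, so 27 after rounding up, against 26 stated.
- Power at 26 per arm = 79.8%, against 80% stated. The design figure is reproduced.

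If 1, 2 or 3 patients leave Arm A and are not replaced, power becomes 79.3%, 78.8% or 78.2%, a loss of 0.5 to 1.6 points. If they are replaced from the allowance of 3 extra patients per arm (16.22), nothing is lost.

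**4. Size for the adverse event tables.** The documents give no rate for DLBCL. Assume that all 58 projected patients are treated, 58 / 2 = 29 per arm.

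| Cases in the arm | Counted | Under 13.4 and 16.323 |
|---|---|---|
| 1 | 1/29 = 3.4% | 0/28 = 0% |
| 2 | 2/29 = 6.9% | 0/27 = 0% |
| 3 | 3/29 = 10.3% | 0/26 = 0% |

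Whatever the true number, the tabulated number is zero.

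**The case against.** **The notes can be read together.** A specific first-cycle rule can sit beside a general one: a lymphoma assumed to be present at baseline did not develop on study. Ineligibility and progression are also different kinds of label, and one patient could carry both. This is a coherent reading, but no text adopts it. If it were adopted, the 11.433 note would have almost nothing left to act on at Day 43.

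**Safety capture does not stop.** Serious events go to the sponsor whether or not they are related (10.4), grade 3 and 4 events are submitted regardless of attribution (10.612), data are due up to confirmation of ineligibility (13.4), and the stopping rule counts treated patients. All of this stands. It limits the loss to the 16.323 tables, which are the safety results the plan sets out to produce.

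**Bias is not demonstrated.** The rule is written in advance for both arms, enrolment is limited to untreated MBL or Rai 0-I disease, and the window is about six weeks. This largely stands, and no direction of bias can be claimed. The arms are not quite alike, however: Arm A starts treatment on Day 1 and Arm B receives nothing until the Day 15 vaccine. A diagnosis before Day 15 therefore falls under the treated branch of 13.4 in Arm A and the untreated branch in Arm B.

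**Disease status is barely touched.** For CLL, the responder comparison in 16.321 pools stable and progressive disease, so recoding one to the other does not change it. This stands. The descriptive distribution, and the progression split for MBL, would still change.

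**A stronger reading is tempting.** A reader might infer that the rule deletes the event from every analysis, or that the disease-status set is also limited to eligible patients. The documents do not say so: 16.321 covers each patient, and 16.322 and 16.33 state no eligibility limit. The event may be lost from these in practice, because the patient moves directly to a monitoring phase that has been dropped, but that is an inference and not a stated rule. Nor is 1/26 = 3.8% the right measure: 26 is the number evaluable for vaccine response, not the safety or progression denominator.

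**Conclusion.** The point holds in a limited form and should be corrected. The 13.4 and 11.433 notes conflict as written. Through the eligibility limits in 16.11/16.311 and 16.323, the 13.4 presumption removes a treated patient with first-cycle DLBCL from the primary response set (if vaccinated) and from the adverse event tables, on the basis of something that happened after randomisation. Handling in time to treatment and the correlative analyses is unspecified, and disease status is not restricted by the text.

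The effect on power is negligible. The cost is to safety reporting: one case would be about 3.4% of an arm, shown as zero. That figure assumes 29 treated per arm and that the first cycle is Days 1-42. How often it would occur cannot be estimated from the documents; it is likely to be rare.

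**What to change.** - **13.4 and 11.433:** reconcile the two notes. Remove the automatic presumption, so that ineligibility for DLBCL rests on the main 13.4 test, a determination that the criterion was not met at registration. Define the first cycle in days for both arms.
- **16.323:** tabulate adverse events by arm in all patients who started treatment, regardless of later eligibility rulings.
- **16.321:** list any first-cycle DLBCL by arm and count it in the disease-status summary.
- **16.311:** no new rule is needed. A vaccinated patient kept in the primary set falls under the existing provision that missing OPA titers count as non-response.

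The cost is a few sentences of text. The adverse event change uses data that 13.4 already requires up to confirmation of ineligibility. The one downside is that a patient kept in the primary set may count as a non-responder if the Day 43 sample is missing; avoiding that means collecting the sample.
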